7.6. Procedure at Disease recurrence

On confirmation of disease recurrence by imaging, participants should receive relapse treatment/management as per standard of care.

At the time of disease recurrence, participants will discontinue protocol surveillance but follow-up data collection documenting relapse details, relapse treatment, any subsequent relapse/progression, and survival should continue unless the participant has explicitly withdrawn consent for this. Follow-up should be approximately 6-monthly, but can be timed to align with routine care visits.

7.7. Change in Participation Status

Participants may choose to change, reduce or stop their participation after joining the trial. Changes may also be made at the discretion of the Principal Investigator. If a participant chooses to change their participation in OTIS-S, the local investigator should explore what level of engagement the participant is willing to continue (with a preference for collecting as complete data as possible).

Within OTIS-S the following changes in participation are possible:

- Stopping miRNA surveillance - but agrees to data being submitted from trial visits.
- Stopping trial-specific follow up – but agrees to data being submitted from routine visits/medical records.
- Stopping donated samples being used in OTIS-S research/analysis (this only applies to miRNA samples used for retrospective analysis).
- Stopping future sharing of data/samples.
- Withdrawal of consent for any further data to be submitted – data up to the point of withdrawal will be retained as described in the participant information sheet.

Changes in participation should be led by the participant and no assumptions should be made on their behalf. A change in participation status form should be submitted to ICR-CTSU to report the details of the reduction in participation. For further guidance on the types of change in participation status, and guidance on loss of contact, please refer to trial guidance notes.

Note that, if a patient becomes pregnant during participation in the trial, they are able to continue in the trial (unless they wish to withdraw as above). However, this should be discussed with the Chief Investigator or delegate to agree appropriate adaptations to the imaging protocol.

7.8. Schedule of Assessments

The following table describes the trial assessments during Part A. Full details of required assessments during Part B of the trial will be confirmed in a protocol amendment prior to commencement of Part B. Part B assessment schedules will be similar, except that patients will have miRNA monitoring (without routine radiological assessment) or standard imaging-based surveillance (no miRNA monitoring) according to random allocation. Full details will be confirmed in a protocol amendment prior to commencement of Part B.

7.8.1. PART A

| Visit/Assessment | Registration ³ | Timepoint post registration | | | | | | | | | | | | | | Disease recurrence |
|--|---------------------------|-----------------------------|----------|----------------|----------------|----------------|-----------|----------------|-----------|-----------|-----------|----------------|-----------|-----------|-----------|--------------------|
| | | 3 months | 6 months | 9 months | 12 months | 15 months | 18 months | 21 months | 24 months | 30 months | 36 months | 42 months | 48 months | 54 months | 60 months | |
| Medical history | X | | | | | | | | | | | | | | | |
| Physical examination | X | | | | | | | | | | | | | | | |
| Tumour markers (AFP, β-HCG, LDH) | X | X | X | X | X | X | X | X | X | X | X | X | X | X | X | |
| miRNA blood sample ¹ | X | X | X | X ⁴ | X | X ⁴ | X | X ⁴ | X | X | X | X ⁴ | X | | X | X ^{4,5} |
| Radiological assessment ² | X | | X | | | | X | | | | X | | | | | |
| Serious Adverse Event assessment | X | X | X | X | X | X | X | X | X | X | X | X | X | X | X | |
| PRO questionnaires (Acceptability questionnaire) | | | | | X ⁶ | | | | | | | | | | | |
| Radiological scan and report upload | | | | | | | | | | | | | | | | X |

1. BD Vacutainer™ SST™ II Advance Tubes, 5ml tube.
2. Cross-sectional abdominal imaging (MRI preferred). For dysgerminoma participants under 19, US may be used at physician's discretion. Some additional imaging, as detailed in section 7.2, in accordance with local practice is permitted. Ideally the same imaging modality should be used for surveillance throughout the trial.
3. Assessments to be completed within 14 days after participant registered into OTIS-S (see section 7.1.1 for exceptions).
4. Samples analysed retrospectively in event of relapse; results not sent to centres in real time.
5. miRNA sample to be taken if not performed within 2 weeks of the confirmatory imaging.
6. Acceptability questionnaire (16 and over only) emailed or posted to participant's home address directly from ICR-CTSU, based on participant's preference.

8. PATIENT-REPORTED OUTCOMES

8.1. Administration of (e)PRO booklets

Participants will be asked at trial entry whether they prefer electronic completion or paper completion of the questionnaire. The PRO questionnaire will only be administered to participants 16 and over only.

Paper PRO completion

Paper versions of questionnaires will be sent out to the participant's address by the ICR-CTSU team. A pre-paid envelope will be included for the participant to return the questionnaire to the OTIS-S trials office.

Electronic PRO completion (ePRO)

Participants who have indicated a preference for electronic completion will be provided with login details and will receive email notifications and reminders when the questionnaire needs completing.

8.2. Part A PRO Schedule

During Part A the only PRO assessment is an acceptability questionnaire to be completed by participants at 12 months post-registration.

8.3. Part B PRO schedule

Additional PRO assessments will be added during Part B of the trial, aimed at assessing the impact of different monitoring approaches on anxiety, fear of recurrence and health-related quality of life. Full details of the PRO schedule will be confirmed in a protocol amendment prior to commencement of Part B. Administration will be coordinated by the ICR-CTSU following the process described above.

9. STUDY INTERVENTION

9.1. miRNA blood sample collection

All blood samples taken for miRNA testing will comprise of 1 blood sample (5ml) collected in 1 tube at each time point. The majority of blood samples will be taken at the same time as routine blood collection.

9.1.1. PART A Sample scheduling

Blood samples for miRNA testing will be collected at all protocol-mandated visits, with the exception of the 54-month visit, timed from registration as follows: registration, 3 months (m), 6m, 9m, 12m, 15m, 18m, 21m, 24m, 30m, 36m, 42m, 48m, 60m.

Samples collected at registration, 3m, 6m, 12m, 18m, 24m, 30m, 36m, 48m and 60m will be analysed in real time and results fed back to the centre. Samples collected at the other time points will be analysed retrospectively at the end of Part A for participants who relapsed during the trial. Results from these samples will not be fed back but will be used to provide more detailed information of the potential lead time for relapse detection on miRNA when compared with imaging.

9.1.2. Storage, labelling and postage of miRNA blood samples

All OTIS-S trial samples should be collected, processed, labelled, stored and shipped as detailed in the OTIS-S Laboratory Manual. All samples must be labelled with the participant's unique trial identifier (Trial ID, as applicable), date of birth and date of sample collection to enable cross-referencing.

9.1.3. Reporting of miRNA blood sample results to centres

For all samples analysed in real-time, miRNA results will be available on the dedicated section of the trial clinical database normally within 2 weeks of the samples being received by the central lab. More details on the data entry by the lab and access procedures for the centres will be available in the trial guidance notes.

9.2. Imaging

For participants who relapse and participants with a positive miRNA result not confirmed by imaging, copies of the MRI/CTs performed throughout the course of the trial will be collected for central review. Centres will transfer the anonymised scans and associated radiology reports by IEP (Image Exchange Portal) to their designated reviewer as described in the OTIS-S trial guidance notes. Ideally the same imaging modality should be used for surveillance throughout the trial.

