11. STATISTICAL CONSIDERATIONS

11.1. Statistical Design, Intervention Allocation and Sample Size Justification

11.1.1. Part A Statistical Design

Part A will use a phase II, A'Hern single arm design³⁷ with all participants receiving the intervention (miRNA monitoring) alongside standard surveillance imaging.

The aim is to demonstrate that miRNA sensitivity exceeds a pre-specified threshold and, hence, sample size is driven by the number of relapses. The sample size is based on the combined cohort (seminoma and dysgerminoma), since differences are not anticipated, and this will allow more timely progression to Part B.

Sensitivity of miRNA for relapse detection is expected to be at least 95% based on previous studies³⁰. Sensitivity >75% is deemed appropriate to warrant further study (i.e. progression to Part B) and, ultimately, the aim is to demonstrate that sensitivity exceeds 85%. For this phase II evaluation, a one-sided alpha of 0.2 will be used. The higher “false positive” risk associated with using a higher alpha than might traditionally be used will facilitate a timely decision regarding initiation of the Part B which will provide a confirmatory evaluation. Subsequent analyses of the Part A cohort, when more relapses have been observed, will achieve greater precision in estimating sensitivity.

In order to have 80% power to show sensitivity >75%, with one-sided alpha of 0.2, a total of 11 relapses need to be observed. If at least 10 of these are correctly identified on miRNA at the same time or before being identified on imaging, a sensitivity $\leq 75\%$ could be excluded. Two further analyses will be performed when 21 and 28 relapses have occurred with the aim of showing sensitivity >80% and >85% respectively, requiring at least 19 of 21 and at least 26 of 28 relapses to be detected on miRNA. Power for both of these analyses (using one-sided alpha of 0.2) will be >80%. Calculations were performed using Stata version 17.0.

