11.2. Endpoint Definitions

11.2.1. Part A Primary Endpoint

The primary endpoint for Part A is sensitivity of miRNA for relapse detection, defined as the number of relapses detectable on miRNA testing before or at the same time as detection on imaging (or via other components of standard surveillance) as a proportion of the total number of relapses identified via standard investigations. In all cases, date of detection will be taken to be the date of the sample collection or imaging/investigation (rather than the date the results were available) and a 2-week window will be allowed from detection on imaging/standard investigations to allow for scheduling of miRNA testing sometimes occurring after imaging. Detection on miRNA requires a positive result according to lab-specific normal ranges, and the date of sample collection will be taken to be the date of relapse detection.

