11.3.3. Part A Analysis Plan

Part A analyses will be largely descriptive. Sensitivity of miRNA will be presented with a 60% exact binomial confidence interval (CI), reflecting the design; 95% CIs will also be presented.

Time from blood draw to miRNA results being available will be summarised (median, interquartile range, range), both overall and by centre, and the proportion of results available within 2 weeks will be presented with a 95% CI. Adherence to miRNA testing and surveillance imaging will be presented as number (proportion) for each time point and also summarised at the patient level (i.e. number missing at least one test or scan). MiRNA results at each time

point will be summarised (negative, positive, or indeterminate) as well as the numbers of samples that could not be analysed.

Acceptability questionnaires will be scored and analysed using the methods described by Sekhon et al³⁵. Items assessing burden and opportunity costs will be reverse scored so that a higher score always indicates higher acceptability. For each patient, a single acceptability score will be computed as the total mean score for the seven items from the theoretical framework of acceptability; the general acceptability item and any trial-specific items will be reported separately. This will be a descriptive non-comparative analysis, reporting mean and standard deviation (or median and IQR if appropriate) for the composite acceptability score and, for individual items, the number and proportion of patients responding in each category. Responses to the general acceptability item will be correlated with individual items from the framework.

For the final analysis, specificity will additionally be presented with a 95% exact binomial confidence interval. Lead time (from detection on miRNA to detection on imaging) will be calculated considering miRNA results from additional samples, analysed retrospectively in relapsing patients. Central review of imaging for relapsing patients will be used to confirm the time that relapse detection was possible and will inform supplementary analyses considering the impact on estimates of sensitivity and specificity.

The Part A analysis will also incorporate comparison of patient and tumour characteristics of the seminoma cohort with the TRISST trial cohort to confirm the extent of heterogeneity and inform planned analyses in Part B.

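### The central imaging reviewer receives the local radiology reports with the scans and no masked first read is stated, so the supplementary analyses built on that review can inherit the local reading

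*Protocol*

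**What the plan says.** Protocol section 9.2 defines who is reviewed: "For participants who relapse and participants with a positive miRNA result not confirmed by imaging, copies of the MRI/CTs performed" during the trial are gathered for a central read. It also defines what is sent. Centres are to "transfer the anonymised scans and associated radiology reports by IEP (Image Exchange Portal) to their designated reviewer", with a reference to the trial guidance notes for the process. The Part A schedule in section 7.8.1 pairs the two items in one row at disease recurrence, "Radiological scan and report upload".

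Section 11.3.3 gives the purpose: "Central review of imaging for relapsing patients will be used to confirm the time that relapse detection was possible". It adds that the review "will inform supplementary analyses considering the impact on estimates of sensitivity and specificity".

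For the primary endpoint, section 11.2.1 fixes timing without reference to central review: "date of detection will be taken to be the date of the sample collection or imaging/investigation", with a 2-week allowance after detection on imaging. The protocol does not describe the central review as blinded or independent, and it sets no order in which scans and reports are read.

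**The concern.** The review asks a retrospective question: on which scan was relapse first visible? Its value is as a check on the local reading, and a reader who holds the local report cannot provide that check cleanly. Two mechanisms operate:

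- **Hindsight.** The report that called the relapse gives its site and date. The reader then knows where to look on earlier scans, which tends to move detection earlier. That shortens lead time and can only lower miRNA sensitivity.
- **Anchoring.** A negative report on an earlier scan discourages the reader from calling disease there. That keeps the local date and favours miRNA sensitivity. For a participant with a positive miRNA result and a scan reported as negative, the same anchoring keeps the case as a false positive, which works against miRNA specificity.

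Because these pull in different directions, the net bias cannot be predicted or corrected afterwards. An analysis plan cannot repair it either, since an unmasked read cannot be undone.

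The local reading is also open to the miRNA result. Most results go back to centres in real time (sections 9.1.1 and 9.1.3), and a positive result triggers imaging (section 7.4.2). The central review is the one described opportunity for an imaging reference less dependent on that knowledge.

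**Working it through.** The protocol gives no figure for the review itself, so the check traces where the review enters the analysis and how much one changed reading could matter there.

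**1. Where the review enters.** Section 11.3.3 names supplementary estimates of sensitivity and specificity. Section 11.2.1 dates detection by the sample or investigation. Section 11.2.2 defines lead time by the scan date. Sections 11.1.1 and 11.3.1 count relapses found on miRNA no later than on imaging, and no text substitutes a centrally revised date. Central re-dating therefore reaches lead time only if the analysis chooses to use it there, and does not reach the progression criteria.

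**2. The plan's own figures, for context.** Section 11.1.1 states: "In order to have 80% power to show sensitivity >75%, with one-sided alpha of 0.2, a total of 11 relapses need to be observed", with at least 10 of 11 detected. For X ~ Binomial(n, p):

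- P(X ≥ 10 | n = 11, p = 0.75) = 11 × 0.75^10 × 0.25 + 0.75^11 = 0.1549 + 0.0422 = 0.197
- P(X ≥ 10 | n = 11, p = 0.95) = 11 × 0.95^10 × 0.05 + 0.95^11 = 0.3293 + 0.5688 = 0.898
- 19 of 21 against 0.80: alpha 0.179, power 0.915 at 0.95
- 26 of 28 against 0.85: alpha 0.187, power 0.837 at 0.95

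All three agree with the stated one-sided 0.2 and at least 80% power. The design is not in dispute.

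**3. Effect of one re-dated relapse on supplementary sensitivity.** One relapse in 28 is 1/28 = 3.6 points. The lower limit of the 60% exact interval is the 0.2 quantile of Beta(x, n − x + 1):

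| Detected | Proportion | 60% exact lower limit |
|---|---|---|
| 26/28 | 92.9% | 0.853 |
| 25/28 | 89.3% | 0.812 |

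A supplementary estimate at 26/28 would exclude 85%, and one at 25/28 would not. This describes the sensitivity of a supplementary result at the boundary. It is not a change in the decision count.

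**4. When re-dating makes a miss.** Moving imaging detection to an earlier scan turns a detection into a miss only if no miRNA sample up to 2 weeks after that scan was positive (section 11.2.1). Samples are scheduled at the same visits as the required scans (section 7.8.1), so the condition can be checked case by case and will not be met in every re-dated case.

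**5. Size of a re-dating.** Required surveillance scans are at 6, 18 and 36 months (section 7.2.1). The gaps are 18 − 6 = 12 and 36 − 18 = 18 months. These are upper cases, because section 7.2.1 allows up to 4 further cross-sectional time points, section 7.4.2 adds triggered imaging, and section 7.5 repeats equivocal imaging at 3 months or as per local practice.

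**6. Specificity.** Assume about 260 − 28 = 232 non-relapsing participants, all evaluable. Reclassifying one unconfirmed miRNA-positive participant as a relapse removes one false positive and raises specificity by at most 1/232 = 0.4 points. The effect is small.

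**The case against.** The strongest reply has four parts.

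- **Guidance notes.** Section 9.2 refers the transfer to trial guidance notes that are not shown. Receiving a report is not the same as reading it first, and those notes might set a reading order. This stands as a possibility. However, the protocol itself says what is sent, and it sends the reports straight to the reader.
- **No contradiction.** The protocol never claims a blinded or independent review. This stands: the point concerns a weak procedure, not an inconsistency.
- **Progression criteria.** A reader might infer that a biased re-read could flip the 10/11, 19/21 or 26/28 decision. The documents do not support that: those counts rest on the date of the detecting investigation, and the review is tied to supplementary analyses. A reader might also infer that re-dating can readily turn a miss into a detection. That would need a later detection date, and protocol surveillance stops at recurrence (section 7.6), so realistic re-dating is mostly earlier.
- **Limits of masking.** Only relapsers and unconfirmed miRNA-positive participants are sent, so selection itself is informative and full masking to relapse status is not achievable with these scans. Knowing the relapse site is also partly inherent in asking when detection was possible. Both stand. They are reasons to add a reconciled read, not to omit a first read without reports.

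A reader might further infer that the reviewer is given miRNA results. Section 9.2 lists only scans and reports. A report on a triggered scan could mention the reason for the request, but that is inference; the text simply does not rule it out.

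**Conclusion.** The point holds in a limited form. Sending local reports with the scans, with no stated first read without them, exposes the central review to anchoring and hindsight and weakens it as a check on local reading. The consequence is confined to the supplementary sensitivity and specificity analyses, and to lead time if re-dated scans are used there. In that setting one relapse in 28 is worth 3.6 points of sensitivity, and a re-dating could shift a date by up to 12 or 18 months where no additional scan intervenes. The net direction of bias is unknown.

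This rests on two assumptions: that the guidance notes do not already require a read before the reports are opened, and that about 28 relapses are available at the final Part A analysis, as section 11.3.1 expects. It is a cheap improvement to a supporting analysis, not a defect in the Part A decision.

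**What to change.** In section 9.2, state that the same designated reviewer first reads each participant's scans in date order without local reports or miRNA results, and records and locks the earliest scan on which relapse is visible, or that none shows it. The reports are released only after the lock, for reconciliation. In section 11.3.3, base the supplementary analyses on the locked read, report the reconciled read alongside, and say whether either is used for lead time.

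This does not hide the fact that a case was selected. At the first read it does hide the site and date of the local call, and whether the case was sent as a relapse or as an unconfirmed miRNA positive.

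No extra scans or readers are needed. The cost is that reports travel separately or later, and the review takes two steps and slightly longer. The change must be in place before central reads begin.

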9.3. Supportive care

All medication considered necessary for the participants' welfare and which is not expected to interfere with the evaluation of the intervention may be given at the discretion of the investigator. All medications (including start/stop dates, dose frequency, route of administration and indication), must be recorded in the participant's clinic notes, as well as the appropriate pages of the eCRF.

10. Safety Reporting

As the study intervention in OTIS-S is limited to blood draws, imaging scans and questionnaire completion, reporting requirements for OTIS-S are limited to direct study-related procedure SAEs as defined in Section 10.1.

10.1. Definitions

Adverse Event (AE)

An AE is any untoward medical occurrence in a trial participant receiving a study intervention; the event does not necessarily have a causal relationship with the procedure. Study interventions for OTIS-S are limited to blood draws and scans, i.e. CT, MRI or ultrasound scans. Adverse events not meeting the criteria of serious will not be collected.

Serious Adverse Event (SAE)

An SAE is any untoward medical occurrence that occurs from baseline and within 30 days of the last study intervention (in OTIS-S this will be the blood draws and imaging assessments performed during follow-up) and:

- results in death

- is life-threatening
- requires hospitalisation or prolongation of existing inpatients' hospitalisation
- results in persistent or significant disability or incapacity
- is a congenital anomaly or birth defect

Important adverse events that are not immediately life-threatening or do not result in death or hospitalisation but may jeopardise the subject or may require intervention to prevent one of the other outcomes listed in the definition above, may also be considered serious.

Progression of the indicated disease and death due to progression of the indicated disease are not considered SAEs.

Definitions of causality

| Relationship | Description |
|----------------|--|
| Unrelated | There is no evidence of any causal relationship with the trial procedure. |
| Unlikely | There is little evidence to suggest there is a causal relationship (e.g. the event did not occur within a reasonable time after administration of the trial procedure). There is another reasonable explanation for the event (e.g. the patient's clinical condition, other concomitant treatment). |
| Possible | There is some evidence to suggest a causal relationship (e.g. because the event occurs within a reasonable time after administration of the trial procedure). However, the influence of other factors may have contributed to the event (e.g. the patient's clinical condition, other concomitant treatments). |
| Probable | There is evidence to suggest a causal relationship, and the influence of other factors is unlikely. |
| Definitely | There is clear evidence to suggest a causal relationship, and other possible contributing factors can be ruled out. |
| Not assessable | There is insufficient or incomplete evidence to make a clinical judgement of the causal relationship. |

Related Unexpected Serious Adverse Event (RU-SAE)

An adverse event that meets the definition of serious and is assessed by the CI or nominative representative as:

- “Related” – that is, it resulted from administration of any of the research procedures, and
- “Unexpected” - for the purposes of OTIS-S all serious and related adverse events will be considered unexpected

